## 15. STATISTICS

### 15.1. Sample Size

Due to the pilot nature of the study, no formal sample size calculations will be conducted. However, to ensure a reliable estimate of the standard deviations to power a future trial with 90% and an expected effect size between 0.3 and 0.7, fifteen people per arm are recommended ([Whitehead-2016](#)). In order to account for a possible attrition rate of 25%, twenty people per arm (total n = 40) will be recruited. In order to ensure adequate data for evaluation, early discontinued subjects may be replaced at Sponsor discretion.

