4.3 Randomization and Blinding

Randomization will occur after confirmation of eligibility and continued subject interest are verified. Subjects will be randomly allocated to either the treatment group (BVR-100) or the control (BES-100) group. Randomization will be assigned via an interactive web responses system (IWRS) in a 1:1 ratio to either BVR-100 or to BES-100.

Once a randomization number has been assigned, it cannot be reused. The randomization schedule will be generated by an independent, non-study biostatistician.

Subjects, Investigators, investigator site staff, persons performing the assessments, clinical operations personnel, data analysts and Sponsor, will remain blinded to the identity of the VR intervention from the time of randomization until database lock and unblinding.

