8.1 General Conventions

Level of significance for statistical tests will be 0.05 two-sided. All analyses will be done using SAS (version 9.4, SAS Institute Inc., Cary, NC, USA).

Safety endpoints will be analyzed in a descriptive manner. Continuous data will be reported using the following descriptive statistics:

- Number of observations (n)
- Mean and Standard deviation (SD)
- Median
- Minimum (min) and Maximum (max)
- 25th percentile and 75th percentile

Categorical data will be presented using frequency (n = number of subjects; m = number of events) and percentage (%).

Listings will be provided for all data recorded in eCRF to study subject profiles. All listings will be sorted by treatment, subject ID and date (if applicable). Unscheduled visit data will only be listed and not included in summaries.

All p-values will be displayed to four decimal places, with p-values less than 0.0001 presented as '<0.0001' and p-values greater than 0.9999 presented as '>0.9999'. Minimum and maximum values will be reported in the units of collection with 3 decimals being maximum value; the mean, median, 25th percentile and 75th percentile will be presented with 1 decimal place more and the standard deviation 2 decimal places more than the units of collection. Percentages for categorical summaries will be represented to 1 decimal place.

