11.17.8 Responder Rate

Responder rate based on the CGI-I score is the proportion of responders at Week 8. Responders are subjects who rated 1 (very much improvement) or 2 (much improvement) in CGI-I at Week 8.

$$\text{Responder Rate} = \frac{\text{Number of responders at Week 8 in a treatment group}}{\text{Total number of subjects in that treatment group in mITT}}$$

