12.9 Exploratory Analyses

12.9.1 Descriptive summaries

Descriptive summary of change from baseline results for total LSAS score and subscores, CGI-S score and PHQ-9 score, and the observed scores will be summarized by treatment groups and week based on ITT population. Observed scores for CGI-I score and PGI-I score will be summarized by treatment groups and week based on ITT population. Descriptive summary of the number of required sessions completed during the study will be summarized by treatment groups based on ITT population. All scores will be listed based on all Enrolled Population

For LSAS summary parameters to be summarized are: LSAS Total Score, Fear of performance situations, Avoidance of performance situations, Fear of social interaction, Avoidance of social interaction, Total fear and Total avoidance. Average of LSAS score will be plotted using line plot by treatment group and week. All listings are based on the Enrolled Population.

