12.9.2 Inferential Summaries

The independent t-test or Mann-Whitney U test will be used to check the significant difference between treatment groups. Exact p-value obtained will be presented in summary tables. Normality test will be performed based on the methods as described in section 12.8.1.2.

Above analysis details are specified in DDP: Table 14.2.4.1, Table 14.2.4.2, Table 14.2.4.3, Table 14.2.5.1, Table 14.2.5.2, Figure 14.2.4.1.

Fisher's Exact Test for Independence of Responders

Since sample size of the responders is expected to be small, the association of responders between the treatment groups will be investigated using Fisher's exact test. Fisher's exact test will be used to compare the proportion of respondents between the treatment groups.

Descriptive statistics and p-values from the test will be provided.

Assumptions

- Variables are categorical.
- All observations are independent.

Reference SAS Program:

```
proc freq data = <INDATA>;
  tables <TESTVAR1>*<TESTVAR2> / fisher;
run;
```

Hypothesis:

H_0 : There is no association between treatment group and responders rate.

vs.

H_1 : There is association between treatment group and responders rate.

Above analysis details are specified in DDP Table 14.2.6.1, Listing 16.2.6.3.1, Listing 16.2.6.3.2, Listing 16.2.6.4, Listing 16.2.6.5, Listing 16.2.6.6, Listing 16.2.6.7

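### Per SAP Section 16, the 7-point CGI-I score is compared between arms only as a responder cut by Fisher's exact test, which has less power than a rank test; SAP 12.9.2 leaves the score's own test unclear

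*SAP*

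**What the plan says.** Protocol 11.3.4 defines CGI-I as seven ordered ratings, from 1 (best) to 7 (worst). SAP 11.17.8 cuts this scale: "Responders are subjects who rated 1 (very much improvement) or 2 (much improvement) in CGI-I at Week 8".

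SAP 12.9.1 plans a description of the full score: "Observed scores for CGI-I score and PGI-I score will be summarized by treatment groups and week based on ITT population".

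SAP 12.9.2 has two parts. It opens with a sentence that a t-test or Mann-Whitney test will be used to compare the arms, without saying which scores this covers. It then turns to responders: "the association of responders between the treatment groups will be investigated using" Fisher's exact test, because few responders are expected.

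The summary table in SAP Section 16 lists, for exploratory endpoints:
- LSAS: description and t-test
- Responder rate: description and Fisher's exact test
- CGI-S, CGI-I, PGI-I and PHQ-9 scores: description only

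SAP 8.1 sets the level: "Level of significance for statistical tests will be 0.05 two-sided".

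**The concern.** Cutting a seven-point scale between 2 and 3 treats a minimally improved subject like one who is very much worse, and a very much improved subject like one who is much improved. That discards ordering already collected at Week 8. Fisher's exact test adds a second loss, because with arms this small its real error rate lies well below 5%.

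Protocol 4.3 and 7.3.1 say that LSAS and the CGI scales are there to give preliminary evidence of effectiveness in line with the next trial's endpoints. If the responder test is the only between-arm test of CGI-I, a non-significant p-value is likely even when the arms differ, and it could be misread as no difference. The SAP also asks for no confidence interval on any CGI-I contrast, and an interval would serve a pilot better than a p-value.

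**Working it through.** **The plan's own figure.** Protocol 15.1 states "fifteen people per arm are recommended", and after 25% attrition "twenty people per arm (total n = 40) will be recruited". Check: 15 / (1 - 0.25) = 20. It reproduces. Neither document states a power for CGI-I or for the responder rate.

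**Inputs from the documents.**
- Two-sided 0.05 (SAP 8.1).
- Allocation "in a 1:1 ratio to either BVR-100 or to BES-100" (SAP 4.3).
- 15 and 20 per arm (Protocol 15.1).
- 52 subjects in the ITT population (SAP Section 13), taken as 26 per arm. The actual split is not given.

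**Inputs assumed.**
- Sham responder rate p_C of 20-40%.
- A latent normal improvement scale shifted by d SD.
- d = 0.3, 0.5, 0.7. Protocol 15.1 mentions "an expected effect size between 0.3 and 0.7", but for a future trial, and the SAP removed it. Here it only sets an illustrative range.
- Category boundaries at z(p_C) + {-0.9, 0, 0.8, 1.7, 2.3, 2.9}, with a wider and a narrower spacing as checks.

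**Formulas.**
- Responder rate on BVR-100: p_T = Φ(Φ⁻¹(p_C) + d).
- Fisher power: the sum over all (x, y) of Bin(x; n, p_C) × Bin(y; n, p_T), counted where the two-sided Fisher p ≤ 0.05. This is exact.
- Mann-Whitney power: simulation, rejecting when (|U - n²/2| - 0.5)/√V > 1.96, with V = (n²/12)[(2n + 1) - Σ(t³ - t)/(2n(2n - 1))] and t the number tied in each category.

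**One cell worked.** n = 20, p_C = 0.30, d = 0.5: p_T = Φ(-0.524 + 0.5) = 0.49. Fisher 15%, Mann-Whitney about 30%, so the loss is about 15 points.

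**Results (p_C 20-40%, base spacing).**

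| n per arm | d | Fisher | Mann-Whitney | Loss (points) |
|---|---|---|---|---|
| 15 | 0.3 | 4% | 11% | 7-8 |
| 15 | 0.5 | 8-9% | 23-24% | 14-15 |
| 15 | 0.7 | 16-18% | 40-41% | 22-25 |
| 20 | 0.3 | 6-7% | 13-14% | 7-8 |
| 20 | 0.5 | 14-15% | 30-31% | 15-17 |
| 20 | 0.7 | 28% | 52-53% | 24-25 |
| 26 | 0.3 | 7-9% | 16-17% | 8-10 |
| 26 | 0.5 | 17-21% | 38-39% | 17-22 |
| 26 | 0.7 | 37-40% | 64-65% | 24-29 |

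Repeat runs used 6,000 to 20,000 trials per cell (standard error at most √(0.25/6000) = 0.65 points). Across them the loss spans about 7-11 points at d = 0.3, 14-22 at 0.5 and 22-29 at 0.7.

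**True size with no difference.** Fisher 1.6-2.8%; Mann-Whitney about 4.4-5.2%. Boschloo's exact test on the same 2×2 table stays within 5% and has 3-12 points more power than Fisher's. So part of the loss is Fisher's conservatism and the rest is the cut itself.

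**Sensitivity.**
- All three spacings and p_C up to 50%: loss 6-10 points at d = 0.3, 12-22 at 0.5 and 20-29 at 0.7.
- p_C = 15% with 26 per arm: up to 33 points at d = 0.7.
- 25% missing Week 8 ratings counted as non-responders (Fisher on 20) against Mann-Whitney on the 15 observed: 13-15 points at 0.5 and 22-26 at 0.7.

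The direction is the same in every cell.

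**The case against.** **The rank test may already be planned.** The first sentence of 12.9.2 excludes no endpoint and follows directly on 12.9.1, which lists the CGI-I score. The Section 16 table is also abbreviated: it gives CEQ only a t-test although 12.8.1.2 allows Mann-Whitney, and it places C-SSRS in the Safety Population although 12.10.5 says ITT. This stands. A reader might infer that the SAP definitely rules out a test on the score; the documents do not settle it, and the Data Display Plan that might is not among them. The narrow reading does have support, because Protocol 15.4.2.4 names tests only for LSAS and responder status. Either way, 12.9.2 and Section 16 need to be made to agree.

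**No effect of a stated size is being missed.** A reader might infer that the test would usually miss the effect the protocol expects here. That is not supported. The 0.3-0.7 range belonged to a future trial, is not tied to CGI-I, and was dropped by the SAP (Section 13, item 4).

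**Full-scale information is not absent.** A reader might infer that the plan yields no full-scale estimate. It summarises scores by arm and week, and if means and SDs are shown, a mean difference follows from them. What is missing is a stated contrast with an interval.

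**The responder test is legitimate and the stakes are low.** The responder rate is a protocol-defined endpoint, and the move from chi-squared to Fisher has a stated small-sample reason. Protocol 15.4.2 plans no formal hypothesis testing, and LSAS gets a full-scale test. All of this stands, and it limits the urgency. It does not remove the choice of test, since the SAP does plan p-values for this endpoint.

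**Conclusion.** The point holds as an inexpensive improvement to an exploratory analysis. On the Section 16 table, the only between-arm test of CGI-I is Fisher's test on the responder cut, and the opening of 12.9.2 does not clearly agree with that.

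The power loss of 7-11, 14-22 and 22-29 points at effects of 0.3, 0.5 and 0.7 is conditional on a latent-normal shift, a sham responder rate of 20-40% and 15-26 per arm. None of the rates or distributions comes from the documents.

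The better test does not make this a powered comparison: at 20 per arm it reaches about 30% at 0.5 and just over one half at 0.7. The main gain is therefore a clearly specified full-scale contrast with an interval, and the extra power comes second.

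**What to change.** In SAP 12.9.2 and Section 16:
1. Name the Week 8 CGI-I score as compared between arms by the Mann-Whitney test already coded in 12.8.1.2. Apply it directly, without the Shapiro-Wilk step.
2. Report the probability that a BVR-100 subject has a better rating than a BES-100 subject, counting ties as one half, with a 95% CI.
3. Keep the responder rate as the protocol-defined clinical summary, with a risk difference and 95% CI.
4. If a responder p-value is kept, use Boschloo's exact test in place of Fisher's.
5. State which other exploratory scores the opening sentence of 12.9.2 covers, so that it matches Section 16.

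Cost: a few lines of SAP text, one NPAR1WAY call on data already collected, and a little extra code for the intervals and for Boschloo's test if used. The downside is one more exploratory comparison and a few more lines of output.

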12.10 Safety Analyses

12.10.1 Adverse Events

All Adverse events will be coded using the MedDRA version 26.0 or Higher. All summaries will be summarized by treatment groups and total based on safety population. Total will not be displayed in the table.

12.10.2 Overall Adverse Events

Number and percentage of subjects and number of events will be summarized by treatment groups and total for the following categories:

- Adverse Events
- Serious adverse events
- Related adverse events
- Related serious adverse events
- Unanticipated adverse device effects
- Adverse events led to death.
- Adverse events led to study discontinuation.
- Adverse events by severity
- Adverse events by relationship

All adverse events will be listed by subject and system organ class. Adverse events will be grouped by subjects. AEs leading to death and serious AEs will be listed separately.

Above analysis details are specified in DDP Table 14.3.1.1, Listing 16.2.7.1, Table 14.3.2.1 and Table 14.3.2.2

12.10.3 Summary of Adverse Events by SOC and PT

Number and percentage of subjects and number of events will be summarized by treatment groups and total, system organ class and preferred terms. Percentages will be based on safety population. Adverse events are sorted by the MedDRA Internationally Agreed Order of SOC and descending frequency of preferred term in Total. Total will not be displayed in the table. Preferred terms with the same frequency are sorted alphabetically. The same will be repeated for serious AEs, related AEs, related serious AEs, AEs leading to death and AEs leading to study discontinuation.

Above analysis details are specified in DDP: Table 14.3.1.2, Table 14.3.1.3, Table 14.3.1.4, Table 14.3.1.5, Table 14.3.1.6 and Table 14.3.1.7

12.10.4 Summary of Adverse Events by Relationship and Severity

Number and percentage of subjects in each system organ class, preferred term will be summarized by relationship and severity for adverse events and treatment group. System organ class and preferred term will be displayed by descending order of frequency in “Total”. Total will not be displayed in the table.

For summaries of relationship,

- AEs will be grouped as “related” or “not related.” AEs assessed as “possible,” “probable,” or “definite,” will be grouped as “related.”
- If a subject had multiple occurrences of the same preferred term within a system organ class, then it is counted once with closest relationship under the preferred term within the system organ class.
- If a subject had different preferred terms within the system organ class with different relationship, it is counted once within closest relationship within the system organ class and “Any AE” categories.

For summaries of severity,

- If a subject has multiple occurrences of the same preferred term within a system organ class, then it is counted once with maximum severity under the preferred term within the system organ class.
- If a subject had different preferred terms within the system organ class with different grades of severity, it is counted once within maximum severity grade within the system organ class and “Any AE” categories.

Above analysis details are specified in DDP: Table 14.3.1.8, Table 14.3.1.9

12.10.5 Columbia- Suicide Severity Rating Scale (C-SSRS)

Number and percentage of subjects without suicidal ideation or suicidal behavior, with suicidal ideation, with suicidal behavior, and with suicidal behavior or ideation will be presented by treatment groups based on ITT Population. All C-SSRS data will be listed based on all Enrolled population.

Above analysis details are specified in DDP Table 14.3.3.1 and Listing 16.2.8.1.

13 Changes to Planned Analyses

- 1 Protocol (section 12.3) specifies 'Baseline demographic and clinical characteristics will be compared between groups with the use of the two-sample t-test and the Mann–Whitney test for continuous measurements with and without normal distribution, respectively'. But the statistical testing for baseline characteristics is being waived as per the recent discussion with the sponsor.
- 2 Protocol (section 12.9) mentions an analysis about differences in the mean change from CGI-S baseline score in the CGI-I and PGI-I at Weeks 2, 4, 6, and 8. This analysis is waived as per the recent discussion with sponsor.
- 3 An additional exploratory endpoint number [7](#) regarding the number of required BVR-100 and BES-100 sessions completed, is added in the section 7.4 as per the decision by sponsor clinical team.
- 4 Sentence "to ensure a reliable estimate of the standard deviations to power a future trial with 90% and an expected effect size between 0.3 and 0.7" in section 4.2 Sample Size Justification is removed because it is for future study not for this current study.
- 5 Per-protocol population definition in section 10.5 is updated to consider only ITT population as per the recent discussion with sponsor.
- 6 Baseline clinical characteristics is updated to follow the baseline definition in section 11.10 as per the recent discussion with sponsor.
- 7 In section 10.4, mITT (Modified Intent-to-Treat) population is removed from analysis and ITT population (efficacy population) has been added as per sponsor request. This population will be used for primary and secondary endpoint analysis.

Reason to change [19](#): Per dataset with data cutoff date January 19, 2024 (Data used for Blinded Data Review Meeting), only 24 out of 52 subjects in the Safety Population met the mITT population definition in the CSP (Clinical Study Protocol) due to missing CEQ data. The reasons for missing CEQ data are a 48-hours visit window restriction for CEQ assessment and only 2 CEQ assessments post baseline. To rectify this issue and to ensure all efficacy subjects are included in the final analysis, the team decided to modify the mITT definition in the CSP to ITT which includes all randomized subjects who have at least one VR session. With this change, the ITT population will include all 52 subjects.

14 Index of Tables, Listings and Graphs

Refer BVR100-102_Data Display Plan (Ver:1.00) for the list of Tables, Listings and Graphs.

15 References

- 2 American Psychiatric Association. *Diagnostic and statistical manual of mental disorders (DSM-5 (R))* (5th ed.). Arlington, TX: American Psychiatric Association Publishing; 2013
- 6 ICH. ICH Harmonized Tripartite Guideline: Statistical Principles for Clinical Trials E9. 1998.
- 7 ASA. Ethical Guidelines for Statistical Practice. Prepared by the Committee on Professional Ethics. 1999.
- 8 ICH. ICH Harmonized Tripartite Guideline: Structure and Content of Clinical Study Reports E3. 1995.
- 9 Changes_to_Planned_Analyses_Form BVR100-102_final_30Jan2024.

16 Appendices

Summary of Statistical Analyses

Endpoints	Analysis Population	Analyses
Primary Endpoint		
Credibility / Expectancy Questionnaire (CEQ) scores	ITT Population	Primary: Descriptive summary, Independent t-test
	Per-Protocol Population	Supportive: Descriptive summary, Independent t-test
Secondary Endpoints		
Subject Retention Rate	ITT Population	Descriptive summary
Time-on-task		Descriptive summary
Exploratory Endpoints		
LSAS Overall & Subscores	ITT Population	Descriptive summary, Independent t-test
Responder Rate		Descriptive summary, Fisher's exact test
CGI-S Score		Descriptive summary
CGI-I Score		Descriptive summary
PGI-I Score		Descriptive summary
PHQ-9 Score		Descriptive summary
Safety Endpoints		
Adverse Events	Safety Population	Descriptive summaries on overall AE, relationship, severity etc.
C-SSRS		Descriptive summary

17 Change Log

Version	Author	Change Date	Description	Reviewer	Review Date
1.00	[REDACTED]	31-Jan-2024	First Approved Version	[REDACTED]	31-Jan-2024

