11.10.1 Change from Baseline

Change between baseline and post-baseline result will be calculated as below.

- Change = Result at Visit X – Baseline Result

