12.8 Efficacy Analyses

12.8.1 Primary Efficacy Analysis

12.8.1.1 Descriptive Summaries

The following summaries will be presented by treatment groups based on ITT and PP population. For Credibility, Expectancy, Total CEQ Score separately, descriptive summary of observed and change from baseline results for expectancy and credibility score will be summarized by visit (Baseline, Week 6 and Week 8/EOS). Also, descriptive summary of the total CEQ score and score for each item will be summarized based on treatment groups and visit. Mean Credibility and Expectancy scores will be plotted using line plots by visit. All listings are based on enrolled population.

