12.8.1.2 Inferential Summaries

The independent t-test or Mann-Whitney U test will be used to check the significant difference between treatment groups. Exact p-value obtained will be presented in summary tables.

Normality test

Shapiro-Wilk test will be performed to test the normality of the two treatment groups and p-value will be interpreted. The test also assumes homogeneity of variances between the two treatment groups. Either one of the following tests will be performed:

- If Shapiro Wilk Test p-value > 0.05 then parametric T-Test will be used
- If Shapiro Wilk Test p-value < 0.05 then Mann-Whitney test will be used

Independent t-tests

Independent t-test will be used to compare mean scores (Observed and change from baseline scores) between treatment groups by visit.

Assumptions

- The samples are independent of one another.
- The sample is normally distributed within each of the two treatment groups.
- The variance should be homogeneous in the two treatment groups.

Reference SAS Program:

T-Test

```
proc ttest data = <INDATA>;
  class <TREATMENT>;
  var AVAL;
run;
```

Mann-Whitney test

```
proc npar1way data=<INDATA> wilcoxon;
  class <TREATMENT>;
  var AVAL;
run;
```

Hypothesis:

H_0 : Mean of parameter is the same in two treatment groups.

vs.

H_1 : Mean of parameter is not the same in two treatment groups.

Supportive analysis of the same will be presented for ITT and Per-Protocol population in a separate table.

Above analysis details are specified in DDP: Table 14.2.1.1, Table 14.2.1.2, Table 14.2.1.3, Table 14.2.1.4, Table 14.2.2.1, Table 14.2.2.2, Table 14.2.2.3, Table 14.2.2.4, Figure 14.2.2.5.

All CEQ scores will be listed in Listing 16.2.6.1

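### SAP Section 13's switch from mITT to ITT brings all 52 subjects into the population, but for a given CEQ Baseline definition it adds no CEQ change score, and the CEQ tests report p-values without intervals

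*SAP*

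**What the plan says.** Protocol 15.2 defines mITT as randomized subjects with at least one VR session, a Baseline CEQ and at least one later CEQ. SAP 10.4 replaces it by ITT, which asks only for randomization and one VR session.

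SAP Section 13 gives the reason. At the cutoff, "only 24 out of 52 subjects in the Safety Population met the mITT population definition in the CSP". It explains that "The reasons for missing CEQ data are a 48-hours visit window restriction for CEQ assessment and only 2 CEQ assessments post baseline". The switch is made "To rectify this issue and to ensure all efficacy subjects are included in the final analysis", and the result is that "With this change, the ITT population will include all 52 subjects".

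For the primary endpoint, SAP 12.8.1.1 plans that "descriptive summary of observed and change from baseline results for expectancy and credibility score will be summarized by visit", and SAP 12.8.1.2 adds that "Independent t-test will be used to compare mean scores (Observed and change from baseline scores) between treatment groups by visit". On reporting, it says: "Exact p-value obtained will be presented in summary tables". No interval is named. SAP 11.10.1 defines change as the visit result minus the Baseline result, and SAP 9.1.1 rules out imputation for efficacy endpoints.

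The two documents place the CEQ Baseline differently. Protocol 11.5.3 expects it on the day of the Baseline visit. SAP 11.10 accepts the first value after the first VR session and before Day 7 of Week 1.

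**The concern.** Section 13 names missing CEQ data as the problem and a wider population as the remedy. A wider population creates no CEQ values. For the change-from-baseline tests, the condition that mITT imposed is the same condition that makes a change score computable, so removing it from the population definition leaves those tests where they were.

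This matters because CEQ is the primary endpoint. Protocol 4.3 uses it as a proxy for subject blinding and says the sample size is meant to support reliable evaluation of treatment credibility. Whether the sham is as credible as BVR-100 is a question about how large a difference can be ruled out. A p-value from about 24 subjects, with no interval, answers that poorly. The by-visit tests also leave out information: a subject with a CEQ at one visit but not another contributes nothing where the value is missing, although the two values are likely to be correlated.

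**Working it through.** **Inputs.** 24 and 52 (SAP Section 13); 15 per arm and 25% attrition (Protocol 15.1, SAP 4.2); two-sided 0.05 (SAP 8.1); change formula (SAP 11.10.1); no imputation (SAP 9.1.1). The split by arm, the correlations and the missingness patterns are not in the documents and are assumed below.

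**1. The plan's own figures.** 15/(1 − 0.25) = 20 per arm, 40 in total, as stated. 24/52 = 46.2% met mITT. ITT and Safety have in effect the same definition, so ITT adds 52 − 24 = 28 subjects (53.8%).

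**2. Who can have a change score.** All presence patterns of CEQ, for one fixed Baseline definition:

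| Baseline | Week 6 | Week 8 | mITT | Change W6 | Change W8 |
|---|---|---|---|---|---|
| no | no | no | no | no | no |
| no | no | yes | no | no | no |
| no | yes | no | no | no | no |
| no | yes | yes | no | no | no |
| yes | no | no | no | no | no |
| yes | no | yes | yes | no | yes |
| yes | yes | no | yes | yes | no |
| yes | yes | yes | yes | yes | yes |

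The five patterns that fail mITT give no change score at either visit. This follows from the definitions, so it also holds at database lock if the count moves. Four of the five can still supply an observed score at some visit.

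**3. Precision.** Half-width of the 95% interval for the arm difference, in SDs of the score tested: t(0.975, n1+n2−2) × √(1/n1 + 1/n2).

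- 12/12: 2.074 × √(1/6) = 0.85
- 15/15: 0.75
- 19/19: 0.66
- 22/22: 0.61
- 26/26: 2.009 × √(1/13) = 0.56
- 24 split 10/14: 0.86; split 8/16: 0.90

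**4. Limit on observed scores**, under the definition used for the 24. Each of the other 28 lacks either the Baseline CEQ or both later ones, so none counts at both Baseline and Week 8. Hence n(Baseline) + n(Week 8) ≤ 2 × 24 + 28 = 76 of a possible 104 (73%), and the same holds for Week 6. If all 52 had a Baseline CEQ, Week 6 and Week 8 would each be capped at 24.

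**5. What a repeated-measures analysis could gain.** Assume 26 per arm, data missing completely at random, equal SDs and a common correlation ρ. Take 12 complete and 14 with Baseline only, per arm. With known covariance, the Week 8 variance relative to the observed-case mean is 1 − ρ² × 14/26. At ρ = 0.5 this is 0.865, an SE 7.0% smaller; at ρ = 0.7 it is 0.736, an SE 14.2% smaller. For the change, the variance is (1 − ρ²)/12 + (1 − ρ)²/26 against 2(1 − ρ)/12. At ρ = 0.5 this is 0.0721 against 0.0833 (SE 7.0% smaller); at ρ = 0.7 it is 0.0460 against 0.0500 (4.1% smaller).

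If instead 12 are complete and 14 have no CEQ at all, the gain is zero. Two further patterns were tried. In one, the incomplete subjects split evenly between Baseline only and Weeks 6 and 8 only. In the other, some of the pairs lack one later visit. With estimated unstructured covariance (1,500 simulated trials per pattern), and counting the zero case, the SE reduction runs from 0 to 15% for Week 8 and 0 to 13% for the change.

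**6. LSAS.** The variance of the baseline-adjusted difference relative to the change-score difference is (1 − ρ²)/(1 + k² − 2ρk), with k = baseline SD/follow-up SD. At k = 1 this is (1 + ρ)/2: 0.75 at ρ = 0.5 and 0.85 at ρ = 0.7. At k = 0.7 it is 0.75/0.79 = 0.95 and 0.51/0.51 = 1.00. Because entry requires a screening LSAS of at least 70, k below 1 is plausible.

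**The case against.** Section 13 is not false. It says ITT includes all 52 subjects, and it does; it nowhere claims to restore change scores. If the issue to be rectified is the small population, ITT rectifies it. That stands, and there is no case here for bringing mITT back: ITT is a reasonable basis for LSAS, retention and time-on-task.

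A reader might also infer that a table headed ITT would hide the reduced numbers. The documents do not support that. Protocol 15.3 and SAP 8.1 list the number of observations with the mean and SD, and SAP 12.8.1.1 plans summaries by arm and visit. An approximate interval could be worked out from these.

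Nor is 24 the final count. It is a cutoff count under the protocol rule, and the SAP supersedes the protocol's statistical section. SAP 11.10 may admit more Baseline values. The documents do not say whether CEQs outside the 48-hour window were collected.

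Change scores are only part of the CEQ analysis. Protocol 15.4.2.1 names none, calls the CEQ t tests exploratory, and observed scores bear most directly on sham credibility. This limits the weight of the point. It does not remove it, because SAP 12.8.1.2 does test change scores.

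**Conclusion.** For a given CEQ Baseline definition, the switch to ITT adds no subject to any CEQ change comparison. That is certain from the definitions. Its size is conditional: if 24 stands, each change test has at most 24 subjects, and fewer where Week 6 or Week 8 is missing. The half-width is about 0.85 SD with an equal split, against 0.56 SD with 52. A higher count under SAP 11.10 would narrow this, but that gain would belong to the Baseline definition.

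Two stronger readings go too far. One is that the switch does nothing for CEQ: it may enlarge the observed-score comparisons, although that gain is bounded and could be nil. The other is that the observed-case tests are biased: the documents do not allow that to be judged.

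What should be fixed is the absence of an interval beside the p-values and the unused CEQ values. In a pilot without formal hypothesis testing (Protocol 15.4.2), this is worth correcting but does not undermine the study.

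**What to change.** 1. **Recount first.** Count CEQ pairs by arm and visit under SAP 11.10, and say whether a CEQ outside the 48-hour window counts. Then state in Section 13 that CEQ comparisons are observed-case and that, for a given CEQ Baseline definition, the switch to ITT may add subjects to observed-score comparisons but adds none to change scores.

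2. **Cheap improvement to SAP 12.8.1.2.** Beside the planned tests, report arm differences with 95% confidence intervals. Add a likelihood-based repeated-measures analysis with Baseline, Week 6 and Week 8 CEQ as outcomes (arm, visit, arm × visit; unstructured covariance, or compound symmetry if that does not converge), using every ITT subject with any CEQ. It assumes normal residuals and data missing at random, the latter as in Protocol 15.4.4. The gain is modest and may be nil (about 0 to 15% smaller SE under the assumed patterns and correlations). The planned t-test and Mann-Whitney results stay in the report as a check.

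3. **Free improvement, separate from the CEQ point.** Compare exploratory LSAS adjusted for baseline LSAS. Against change scores, the variance falls by 25% at ρ = 0.5 and 15% at ρ = 0.7 only if baseline and follow-up SDs are equal. With an assumed SD ratio of 0.7 it falls by about 5% and 0%.

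The cost is SAP wording, one recount and a small amount of programming. No new data are needed.
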